## 6.4 Prior and concomitant medications

Prior medications include any medications that started prior to the date of first dose of IMP.

Concomitant medications are medications taken after the first dose of IMP (PSL or OC).

Concomitant medications will be attributed to the treatment in which they start. Thus, for study participants in Part 1 randomized in Sequence A, any medication taken on Day 1 through Day 13 (prior to OC intake) will be attributed to the PSL alone period; any medications taken on Day 13 (after OC intake) through Day 34 (prior to OC intake) will be attributed to the PSL+OC period and any medication taken on Day 34 (after OC intake) through Day 44 will be attributed to OC alone. For study participants in Part 1 randomized in Sequence B, any medication taken on Day 1

through Day 18 (prior to PSL intake) will be attributed to OC alone; any medications taken on Day 18 (after PSL intake) through Day 30 (prior to OC intake) will be attributed to PSL and any medication taken on Day 30 (after OC intake) through Day 46 will be attributed to PSL+OC. For study participants in Part 2 randomized in Sequence A, any medication taken on Day 1 through Day 9 (prior to OC intake) will be attributed to the PSL alone period; any medications taken on Day 9 (after OC intake) through Day 26 (prior to OC intake) will be attributed to the PSL+OC period and any medication taken on Day 26 (after OC intake) through Day 40 will be attributed to OC alone. For study participants in Part 2 randomized in Sequence B, any medication taken on Day 1 through Day 18 (prior to PSL intake) will be attributed to OC alone; any medications taken on Day 18 (after PSL intake) through Day 26 (prior to OC intake) will be attributed to PSL and any medication taken on Day 26 (after OC intake) through Day 42 will be attributed to PSL+OC.

A schematic summary is given below:

Study Part	Sequence	PSL alone	PSL + OC	OC alone
1	A	Day 1 – 13 (prior to OC intake)	Day 13 (after OC intake) – 34 (prior to OC alone intake)	Day 34 (after OC intake) - 44
	B	Day 18 (after PSL intake) – Day 30 (prior to OC intake)	Day 30 (after OC intake) - 46	Day 1 – 18 (prior to PSL intake)
2	A	Day 1 – 9 (prior to OC intake)	Day 9 (after OC intake) – 26 (prior to OC intake)	Day 26 (after OC intake) - 40
	B	Day 18 (after PSL intake) – 26 (prior to OC intake)	Day 26 (after OC intake) – 42	Day 1 – 18 (prior to PSL intake)

If a medication started prior to IMP administration (PSL or OC) and stopped after the first IMP administration (PSL or OC) or stopped during the first treatment period (for Sequence A: PSL period; for Sequence B: OC alone period), then that medication will be classified as both prior and concomitant for PSL alone or OC alone period respectively (depending on the randomized sequence).

If a medication starts prior to IMP administration (PSL or OC) and is stopped during the second treatment period (for Sequence A: PSL+OC period; for Sequence B: PSL period), then that medication will be classified as prior and concomitant for both treatment periods (PSL+OC and PSL alone). The same rule will apply for the third treatment period.

Any medications with missing dates and/or times will be handled as described in [Section 4.2.4](#) to classify them as prior or concomitant.

Prior and concomitant medications will be listed by study part for all study participants in the SS. Prior and concomitant medication will be tabulated separately. The summary will be presented by WHODD Anatomical Main Group [Level 1 term text], Pharmacological Subgroup [Level 3 term text] and PT. The reported term will be included in the listing. Tabulation for prior medications will be presented separately for each study part by treatment sequence; tabulation for concomitant medications (PSL+OC concomitant, PSL alone-concomitant and OC alone-concomitant) will be summarized separately for each study part by treatment separately for each treatment sequence.

The prior medication tabulation will be sorted alphabetically by Level 1 term, alphabetical Level 3 term within Level 1 and decreasing frequency of PT in the 'All Participants' column. The concomitant medication tabulation will be sorted alphabetically by Level 1 term, alphabetical Level 3 term within Level 1 and decreasing frequency of PT in the PSL+OC column.

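### SAP 6.4 assigns a pre-dose medication stopped in Sequence B's PSL period to the wrong pair of treatments, and does not settle whether later medications are attributed by start or by overlap

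*SAP*

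**What the plan says.** SAP 6.4 tabulates concomitant medications under three treatments: PSL alone, PSL+OC and OC alone.

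The general rule comes first: "Concomitant medications will be attributed to the treatment in which they start". The section then spells out the windows as a consequence of that rule, but words them by medication taken. For Part 1 Sequence A, "any medications taken on Day 13 (after OC intake) through Day 34 (prior to OC intake) will be attributed to the PSL+OC period". For Part 1 Sequence B, the first window is OC alone and ends at the first PSL dose on Day 18. The second window is worded as follows: "any medications taken on Day 18 (after PSL intake) through Day 30 (prior to OC intake) will be attributed to PSL". The third window is PSL+OC and runs from the Day 30 OC dose to Day 46. A schematic table repeats the windows for both parts.

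A further rule covers medications that began before the first dose. If such a drug stops in the second period, identified as "for Sequence A: PSL+OC period; for Sequence B: PSL period", the SAP's instruction is that the "medication will be classified as prior and concomitant for both treatment periods (PSL+OC and PSL alone". A closing sentence extends this: "The same rule will apply for the third treatment period". Medications begun after the first dose have no equivalent carry-forward rule.

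**The concern.** The rule for pre-dose medications recognises that the second period differs by sequence, yet gives one pair of treatments for both sequences. The pair fits only the order in Sequence A. Programmed as written, it produces wrong entries for Sequence B: a drug appears beside a treatment given after it was stopped, and is missing from one during which it was taken.

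The second problem is that two attribution principles sit in one paragraph. Starting in a window and being taken in a window are the same thing for a short course inside one window. They differ for a course that crosses a window boundary. Two programmers working from this text could produce different tables.

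What is at stake is whether the concomitant-medication tables show what was on board with each treatment. SAP 3.9 created the three groups for that purpose. Paracetamol, ibuprofen, inhaled corticosteroids and treatment for adverse events are permitted (Protocol 6.5.1 and 6.5.2), so relevant records can arise.

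**Working it through.** The plan states no figure here, so the check compares each rule with the SAP's own calendar.

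**Inputs.** Windows from the SAP 6.4 text and schematic table, in order of occurrence:

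| Part, sequence | First | Second | Third |
|---|---|---|---|
| 1, A | PSL alone, Days 1–13 | PSL+OC, Days 13–34 | OC alone, Days 34–44 |
| 1, B | OC alone, Days 1–18 | PSL alone, Days 18–30 | PSL+OC, Days 30–46 |
| 2, A | PSL alone, Days 1–9 | PSL+OC, Days 9–26 | OC alone, Days 26–40 |
| 2, B | OC alone, Days 1–18 | PSL alone, Days 18–26 | PSL+OC, Days 26–42 |

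Boundary days are split at the dose that opens the next window.

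**Check 1: drug begun before the first dose, stopped in the second window.** It overlaps the first and second windows.

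| Part, sequence | Actual overlap | Rule assigns | Wrongly added | Omitted |
|---|---|---|---|---|
| 1, A | PSL alone, PSL+OC | PSL alone, PSL+OC | none | none |
| 1, B | OC alone, PSL alone | PSL alone, PSL+OC | PSL+OC | OC alone |
| 2, A | PSL alone, PSL+OC | PSL alone, PSL+OC | none | none |
| 2, B | OC alone, PSL alone | PSL alone, PSL+OC | PSL+OC | OC alone |

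Example: a Part 1 Sequence B drug running from before Day 1 to Day 25 stops 30 − 25 = 5 days before the OC dose that opens PSL+OC. The error arises for any stop within 30 − 18 = 12 days in Part 1, or 26 − 18 = 8 days in Part 2.

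**Check 2: drug begun after the first dose and still ongoing at the dose opening the next window.** Each of the four part-by-sequence cells has two boundaries, so 4 × 2 = 8 cases.

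| Part, sequence | Starts in | Ongoing at | Start wording gives | Taken wording gives |
|---|---|---|---|---|
| 1, A | PSL alone | Day 13, OC dose | PSL alone | PSL alone, PSL+OC |
| 1, A | PSL+OC | Day 34, OC dose | PSL+OC | PSL+OC, OC alone |
| 1, B | OC alone | Day 18, PSL dose | OC alone | OC alone, PSL alone |
| 1, B | PSL alone | Day 30, OC dose | PSL alone | PSL alone, PSL+OC |
| 2, A | PSL alone | Day 9, OC dose | PSL alone | PSL alone, PSL+OC |
| 2, A | PSL+OC | Day 26, OC dose | PSL+OC | PSL+OC, OC alone |
| 2, B | OC alone | Day 18, PSL dose | OC alone | OC alone, PSL alone |
| 2, B | PSL alone | Day 26, OC dose | PSL alone | PSL alone, PSL+OC |

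The wordings disagree in all 8 cases. In 6 the boundary is an OC dose: the start wording leaves out PSL+OC in 4 and OC alone in 2. In the other 2 the boundary is a PSL dose and PSL alone is left out. The taken wording leaves out nothing.

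**After correction.** With a sequence-specific pair, check 1 agrees with actual overlap in all 4 cells. With one overlap rule, none of the 8 cases in check 2 loses a window.

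**The case against.** The best defence of the pre-dose rule is that its intent can be recovered. The sentence names Sequence B's second period correctly and speaks of both periods, and the schematic gives the order. The preceding sentence, on pre-dose drugs stopped after the first dose, could also be read as restoring OC alone for Sequence B. That softens the omission but does not remove the false PSL+OC entry. No reading of the stated pair fits Sequence B.

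On the second issue, a reader might infer that the SAP certainly drops every drug ongoing at an OC dose. The documents do not support that. Pre-dose drugs are carried forward, and the taken wording would place paracetamol begun on Day 12 and continued past the Day 13 OC dose under PSL+OC. Two things do favour the start reading: the windows are presented as following from the start rule, and a carry-forward for pre-dose drugs would be unnecessary if overlap already governed. The text therefore contradicts itself, and the outcome depends on which wording is programmed.

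The objections on reach largely stand. Protocol 5.2 (criterion 15) and 6.5.2 bar most medication before dosing and during treatment, so few records may qualify. All prior and concomitant medications are also listed for the Safety Set, so the information is not lost. Neither the PK Set definition (SAP 3.5.3) nor the primary model (SAP 9.1) uses these tables.

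**Conclusion.** The point holds as two wording defects in SAP 6.4. The pre-dose rule is wrong as written for Sequence B. The attribution of drugs begun after the first dose is contradictory.

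Both are confined to descriptive tables. SAP 1 restricts reporting to Part 1 and a subset of outputs, and does not say whether these tables are in the subset. The first error needs a Sequence B participant with a pre-dose drug stopped in the PSL period. Since 7 of the 14 Part 1 completers are in Sequence B (SAP 2.2), 7 is the ceiling among completers. Dosed non-completers, whose number is not given, could add to it. The true count could be zero. The number of drugs affected by the second defect cannot be derived from the documents.

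A reader might go further and infer that all of Sequence B is misclassified, that the OC-alone and PSL+OC columns cannot be compared, or that the EE/LN interaction result is at risk. None of these follows, given the narrow trigger, the full listing and the absence of any link to the PK analyses. The length of the PSL+OC window relative to the OC sampling days is a separate matter that neither rule causes.

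The conclusion assumes that the rules are programmed literally and that the schematic windows are the intended ones.

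**What to change.** Make two edits to SAP 6.4:

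1. Make the pair for a pre-dose drug stopped in the second period sequence-specific: PSL alone and PSL+OC for Sequence A; OC alone and PSL alone for Sequence B.
2. Replace the start and taken wordings with one rule: a medication is concomitant for every interval in the schematic table that its start-to-stop dates overlap, whenever it began. This also makes explicit what applies to the third period.

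The cost is a short text change and a small programming change, using dates the existing rules already need. The one downside is that a medication can count in more than one column, which a table footnote should state. A flag for medications overlapping the OC sampling days is optional and is not needed to correct the error.

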## **7 MEASUREMENTS OF TREATMENT COMPLIANCE**

Administration of study medication will be performed under the supervision of the Investigator (or designee). Compliance will be monitored by drug accountability. A Drug Accountability form will be used to record study medication dispensing and return information on a by-study participant basis. Drug administration/consumption will be recorded and any discrepancies with the dosing regimen will be explained. Dosing deviations will be included in the listing of IPDs where applicable.

No formal calculations of compliance will be presented as all study medication is administered on site.

## **8 EFFICACY ANALYSES**

Not applicable.

## **9 PHARMACOKINETICS AND PHARMACODYNAMICS**

The calculation of the PK parameters of EE, LN, PSL and its metabolites ([REDACTED] [REDACTED]) and [REDACTED] ([REDACTED]) will be performed by the Pharmacokinetics, Pharmacodynamics, Modeling and Simulation Department, ICON PLC. All PK TFLs will be produced by ICON PLC SAS programming (Early Phase) or ICON Biostatistics. All PK tables and figures will be produced separately for each study part. All PK listings will be presented by study part.

Pharmacokinetic parameters of EE, LN, PSL and its two metabolites ([REDACTED] [REDACTED]) will be computed using the actual sampling time points.

The individual time-plasma concentrations of EE, LN, PSL, PSL metabolites, and PK parameters of EE, LN, PSL and PSL metabolites will be summarized by treatment (for EE and LN: OC alone and PSL+OC; for PSL and its two metabolites: PSL+OC and PSL alone) using descriptive statistics (number of observations, geometric mean, lower and upper 95% confidence intervals [CI], geometric coefficient of variation [CV], arithmetic mean, standard deviation [SD] and CV, median, and minimum and maximum value) and graphical displays. During the PSL + OC treatment period, two sets of PSL PK parameters will be analyzed: one set when PSL is

administered alone and the other set when PSL is administered with OC. Two sets of EE and LN PK parameters will be analyzed: one set during the PSL+OC treatment period and another during the OC alone treatment period.

All PK sampling time deviations will be calculated relative to the last dose of study medication. For sequence A, it will be on Day 19 for the PSL+OC period and on Day 34 for the OC alone period. For sequence B, it will be on Day 1 for the OC alone period and on Day 36 for the PSL+OC period. Any samples that are obtained outside the tolerance window permitted at the specified time point will be discussed at the DEM and any possible exclusion from analysis will be documented accordingly.

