8.1 Pharmacokinetics

Whole blood will be collected for measurement of plasma concentrations of PSL as specified in the Schedule of Activities. Additional samples may be collected at additional time points during the study if warranted and agreed upon between the Investigator and the Sponsor.

Instructions for the collection and handling of biological samples will be provided by the Sponsor. The actual date and time (24-hour clock time) of each sample and each dose of OC or PSL administered will be recorded. Plasma samples will be collected for measurement of plasma concentrations and to evaluate the PK of PSL, EE, and LN as specified in the appropriate Schedule of Activities.

Samples collected for analyses of PSL plasma concentration may also be used to evaluate safety aspects related to concerns arising during or after the study.

Any changes in the timing or addition of time points for any planned study assessments must be documented and approved by the relevant study team member and then archived in the Sponsor and site study files but will not constitute a protocol amendment. The institutional review board (IRB)/independent ethics committee (IEC) will be informed of any safety issues that require alteration of the safety monitoring scheme or amendment of the ICF.

Instructions and additional details regarding PK sampling are provided in the Laboratory Manual.

The maximum deviations from scheduled sampling times considered irrelevant for PK are defined in Table 8–1.

Table 8–1: Irrelevant time deviations for PK sampling

PK blood sampling times	Deviation from scheduled time considered irrelevant
0 hours (predose)	Within 60 minutes
0.25 to 1.5 hours	2 minutes
2 to 8 hours	5 minutes
12 hours	15 minutes
24 to 48 hours	60 minutes

PK=pharmacokinetic

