## 3.2 General study level definitions

### 3.2.1 Relative day

Relative day will be calculated based on the treatment received. Therefore, three relative days are defined, based on treatment with OC alone, PSL alone and the combination of OC and PSL.

The relative day of an event will be derived with the date of first dose of the treatment, as reference. For Padsevonil, this will be Day 1 in Sequence A and Day 18 in Sequence B. For OC alone this will be Day 34 in Sequence A and Day 1 in Sequence B. For the combination of PSL+OC the first dose is given on Day 13 in Sequence A and Day 30 in Sequence B

Relative days for an event or measurement occurring before the date of first dose of treatment are calculated as follows:

$$\text{Relative Day} = \text{Event Date} - \text{Date of First Dose of Treatment}$$

The relative day for an event or measurement occurring on the date of first treatment dose is 1. The relative day for an event or measurement occurring on or after the date of first treatment dose to the date of the last dose will be calculated as follows:

$$\text{Relative Day} = (\text{Event Date} - \text{Date of First Dose of Treatment}) + 1$$

For events or measurements occurring after the date of last treatment dose, relative day will be prefixed with '+' in the data listings and will be calculated as follows:

$$\text{Relative Day} = + (\text{Event Date} - \text{Date of Last Dose of Treatment})$$

There is no relative Day 0. Relative day will not be calculated for partial dates in cases where relative day is shown in a study participant data listing. In such cases, relative day should be presented as '--' in the relevant study participant data listing.

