## **Part 1**

### ***Sequence A (Day 1 to Day 36)***

In Part 1, study participants enrolled in Treatment Sequence A will be administered PSL BID (up-titration to steady-state [400mg BID]) from Day 1 to Day 5, followed by a maintenance period from Day 6 to Day 12 with a single dose of OC administered on the morning of Day 13. A taper of PSL will occur from Day 15 to Day 19. Starting on Day 20, the study participants will then complete a 14-day Washout Period followed by a return to the clinic for the OC-only dosing on Day 34. A SFU Visit will occur between Day 41 and Day 44.

Treatment Sequence A consists of the “PSL+OC Period” followed by the “OC alone Period”.

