### **3.4 Protocol deviations**

Important protocol deviations (IPD) are deviations from the protocol which potentially could have a meaningful impact on study conduct or on the primary PK outcome for an individual study participant. Study participants will be excluded from SS only when there is documented evidence that they received no treatment. Study participants may be excluded from the Pharmacokinetic Set (PKS) if they had an important protocol deviation affecting the PK parameters.

The criteria for identifying protocol deviations and the classification of protocol deviations will be captured in the Important Protocol Deviations document. To the extent feasible, rules for identifying protocol deviations will be defined without review of the data and without consideration of the frequency of occurrence of such deviations. Whenever possible, criteria for identifying important protocol deviations will be implemented algorithmically to ensure consistency in the classification of important protocol deviations across all study participants.

Important protocol deviations will be reviewed as part of an ongoing data cleaning process prior to database lock to confirm exclusion from analysis sets. After all data have been verified/coded/entered into a database, a data evaluation meeting (DEM) will be held.

At least one DEM will be performed at the following time:

- Prior to the final analysis after all data have been verified/coded/entered into the database

Additional DEMs may be conducted as deemed necessary.

The purpose of these DEM reviews will be to review all protocol deviations, determine whether the deviations are considered important or not important, define the analysis sets, and check the quality of the data. The reviews will also help decide how to manage problems in the study participants' data (e.g., missing values, withdrawals and protocol deviations).

Accepted deviations from scheduled time points will be described in the appropriate documents and included in the Study Master File. After the pre-analysis review, resolution of all issues, and documentation of all decisions (including inclusion into each of the analysis sets) at the final DEM, the database will be locked.

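### SAP section 9 measures Part 1 PSL+OC sampling-time deviations from the last taper dose, which comes after every sample in that period

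*SAP*

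**What the plan says.** SAP section 9 gives a general rule: "All PK sampling time deviations will be calculated relative to the last dose of study medication". It then names the days. The Sequence A statement reads: "For sequence A, it will be on Day 19 for the PSL+OC period and on Day 34 for the OC alone period". The matching Sequence B statement reads: "For sequence B, it will be on Day 1 for the OC alone period and on Day 36 for the PSL+OC period". Samples outside their window are taken to the data evaluation meeting (DEM), where exclusion is possible. Section 9 gives neither a formula for the deviation nor the windows.

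The windows are in Protocol 8.1, Table 8-1, described there as "The maximum deviations from scheduled sampling times considered irrelevant for PK". They are 60 minutes predose, 2 minutes from 0.25h to 1.5h, 5 minutes from 2h to 8h, 15 minutes at 12h, and 60 minutes from 24h to 48h.

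Three other places bear on the named days:

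- SAP 3.2.2, Part 1 Sequence A: "A taper of PSL will occur from Day 15 to Day 19". The Sequence B text puts the taper on Days 32 to 36.
- SAP 3.2.1: "For the combination of PSL+OC the first dose is given on Day 13 in Sequence A and Day 30 in Sequence B".
- SAP 3.4: "Accepted deviations from scheduled time points will be described in the appropriate documents and included in the Study Master File".

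**The concern.** A sampling-time deviation means something only when it is measured from the dose that gives the sample its nominal time. On its own, the phrase about the last dose could mean the most recent dose before each sample, which would be sensible for most draws. Naming Day 19 and Day 36 closes off that reading, because those are the final taper days and PK sampling has already ended by then.

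What is at stake is the screen that picks out samples for DEM discussion. It works for the OC-alone (reference) period, where Day 34 and Day 1 are the actual OC dosing days. As written, it does not work for the PSL+OC (test) period of the same participants.

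**Working it through.** **Inputs.** PSL is given for 19 days in Part 1 (SAP 2.2), starting on Day 1 in Sequence A and Day 18 in Sequence B. Sampling days and times come from the footnotes to SAP Tables 2-4 and 2-5, which match Protocol Tables 1-4 and 1-5. In the copy I have, the Sequence A sampling row of SAP Table 2-2 carries Sequence B days, including a Day 19 entry. I treat that as a damaged table and rely on the footnotes.

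**Step 1: reproduce the named days.** Last PSL day = first PSL day + 19 − 1. Sequence A: 1 + 18 = Day 19. Sequence B: 18 + 18 = Day 36. Both agree with SAP section 9, so the SAP has correctly identified the last PSL dose. The error lies in using that dose as the timing reference.

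**Step 2: count the draws in the PSL+OC period.** The count is the same in both sequences.

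- PSL troughs: 5 (Days 2, 4, 6, 8, 10 in A; Days 19, 21, 23, 25, 27 in B).
- PSL profile without OC, Day 12 or 29: predose plus 10 postdose times = 11.
- Profile with OC, Day 13 or 30: predose, 0.25, 0.5, 1, 1.5, 2, 3, 4, 6, 8, 12, 24, 36 and 48h = 14 (the 36h draw is for EE/LN only).
- Total: 5 + 11 + 14 = 30.

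**Step 3: distance from the scheduling dose to the named morning dose.** Distance = (named day − scheduling day) × 24h.

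| Draws | Sequence A | Sequence B | Distance |
|---|---|---|---|
| Profile with OC (14) | 19 − 13 = 6 d | 36 − 30 = 6 d | 144h |
| PSL profile without OC (11) | 19 − 12 = 7 d | 36 − 29 = 7 d | 168h |
| Latest trough | 19 − 10 = 9 d | 36 − 27 = 9 d | 216h |
| Earliest trough | 19 − 2 = 17 d | 36 − 19 = 17 d | 408h |

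The last sample of the period, at 48h, falls 144 − 48 = 96h before the named dose. The earliest trough falls 408h before it. No sample in the period follows the named dose.

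**Step 4: apply the rule literally.** Deviation = (sample time − named dose time) − nominal post-dose time. For an on-time sample h hours after the Day 13 or 30 dose, this is (h − 144) − h = −144h, whatever h is. The profile without OC gives −168h. The troughs, with nominal time zero, give −216h to −408h. The widest window is 60 minutes, so 30 of 30 on-time draws fail in each sequence. If the evening dose is meant, add about 12h (assuming 12h between the two daily doses), which gives 156h to 420h.

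**Step 5: check the OC-alone period.** The OC dose is on Day 34 (A) or Day 1 (B), and the samples are scheduled from that dose. The named reference is right, and on-time postdose draws give a deviation of zero.

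**The case against.** The best case against the point is that it has little consequence. PK parameters are estimated from actual sampling times relative to dosing (SAP 3.1), so the named reference does not enter Cmax or AUC. A screen that puts every test-period sample out by six days or more would be noticed at once at the DEM, which only discusses such samples and need not exclude any. The elements of a correct rule are also present elsewhere: the schedules tie each sample to a dose, Table 8-1 gives the windows, and Protocol 8.1 says that "The actual date and time (24-hour clock time) of each sample and each dose of OC or PSL administered will be recorded". SAP 3.4 places accepted deviations in documents not available here. The study has been stopped, and SAP section 1 limits reporting to a subset of Part 1 outputs. It looks like a drafting slip.

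All of that stands, and it is why the point is minor. None of it makes the stated reference right. If another document holds the correct rule, the SAP contradicts it.

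A reader might go further and infer a count of misclassified samples when an OC dose is given late. The documents do not support one. If actual and scheduled times are both measured from the named dose, that dose cancels and leaves actual minus scheduled clock time, whichever day is named. Any count would then describe a formula the SAP does not state, and would rest on dose delays the documents do not give.

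**Conclusion.** The reference dose in SAP section 9 is wrong as written for the Part 1 PSL+OC period in both sequences, and right for the OC-alone period. Under the literal formula, all 30 scheduled draws per participant fall outside Table 8-1 when taken on time, by 144h to 408h from the morning dose. The screen then could not separate mistimed from correctly timed samples in the test period. This rests on the sampling footnotes, on the named dose being the morning one, and on the literal formula, since the SAP states none.

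Severity is minor. A reader might infer that the primary comparison is biased, or that test-period samples would be dropped more often than reference-period samples. Neither follows: the parameters and geometric mean ratios are not miscalculated, exclusion is at the DEM's discretion, and no unequal exclusion is shown. Nor can the effect be placed around the EE or LN peak, because the documents give no tmax for either. The claim is that the SAP states the wrong reference, not that no working rule exists.

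**What to change.** Replace the sentences naming the days in SAP section 9 with wording to this effect:

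> Each deviation is the actual time since the reference dose minus the nominal time, using the actual time of the dose from which the sample is scheduled. For EE and LN this is the OC dose (Days 13 and 34 in Sequence A; Days 1 and 30 in Sequence B). For PSL and metabolites it is the morning PSL dose of the profile (Days 12 and 13 in Sequence A; Days 29 and 30 in Sequence B). The 24h and 48h PSL samples are timed from the Day 13 or Day 30 dose and must also precede that morning's PSL dose. Profile predose samples and the PSL troughs (Days 2, 4, 6, 8, 10 in Sequence A; Days 19, 21, 23, 25, 27 in Sequence B) are checked against the dose they precede. Tolerances are those of Protocol Table 8-1.

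The 24h and 48h PSL samples need their own sentence because the Sequence A footnote defines them both as postdose times and as predose to the Day 14 and Day 15 doses, while the Sequence B footnote defines them only as predose to the Day 31 and Day 32 doses. Without it, these draws would have two references.

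The cost is one SAP paragraph and the deviation derivation code. The dose and sample times needed are already recorded, and PK estimation and the primary model do not change.
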